#### Objectives

#### Tertiary/exploratory

 To evaluate efficacy of tolebrutinib on disease progression and activity in NRSPMS, assessed by other clinical and imaging measures and by selfreported assessment

#### Endpoints

- Time to onset of sustained 20% increase in the 9-HPT for at least 6 months
- Time to onset of sustained 20% increase in the T25-FW for at least 6 months
- Time to onset of a 4-point decrease in the SDMT, confirmed over at least 3 and 6 months
- The proportion of participants with CDI confirmed over at least 6 months
- The proportion of participants with CDI confirmed over at least 6 months and maintained until the EOS
- Change from baseline to Months 12, 18, and 24 and to the EOS in the EDSS score, T25-FW test, 9-HPT, SDMT, and CVLT-II
- Change from baseline to Months 12, 18, and 24 and to the EOS in modified MSFC-3, assessed as the composite of the T25-FW test, 9-HPT, and SDMT
- Proportion of participants with NEDA-3 at Months 18, 24, 30, 36, and the EOS
- The annualized adjudicated relapse rate (ARR)
- Actigraphic analysis of activity counts and indices of change from baseline to the EOS summarized over time (in a subset of participants)
- Change from baseline of total volume of T2-hyperintense lesions as detected by brain MRI at Months 18, 24, and the EOS
- Total number of new Gd-enhancing T1hyperintense lesions as detected by MRI, defined as the sum of the individual number of new Gd-enhancing T1hyperintense lesions at all scheduled visits starting after baseline up to and including the EOS visit
- Change from baseline by visit in the volume of T1-hypointense lesions and cumulative number of new T1 hypointense lesions
- MTR recovery at EOS in new MTR lesions detected at Months 6 and 12
- Change in number of phase rim lesions in SWI MRI from baseline through the EOS (subset of centers with capacity of 3T MRI)
- Number and volume of slowly evolving lesions (SELs)
- Normalized T1 (nT1) intensity evolution in SELs
- Change in EQ-5D-5L from baseline by visit over time
- To evaluate the treatment effect of tolebrutinib via changes in participants' health-related quality of life (HRQoL), and working capacity

#### 1.2.1 Estimands

The primary estimand for the primary endpoint is summarized in Table 2. More details are provided in Section 3.

In all analyses, the comparison of interest will be the comparison of tolebrutinib versus placebo.

Statistical Analysis Plan SAR442168-EFC16645 - tolebrutinib 30-Apr-2024 Version number: 3

Endpoint	Estimands			
Category (estimand)	Endpoint	Population	Intercurrent event(s) handling strategy	Population-level summary (Analysis and missing data handling)
Primary objective: To	evaluate the efficacy of tole	ebrutinib compared to	placebo in delaying disability progression in NRSPMS	
Primary endpoint (treatment policy estimand)	Time from randomization to onset of 6-month CDP	ITT	Regardless of completion of the treatment period (treatment policy)	Treatment effect on time to onset of 6-month CDP, as measured by the hazard ratio for tolebrutinib compared to placebo, analyzed by a Cox proportional hazards model with terms for treatment group, age at screening (>40, ≤40 years), geographical region (US, non-US), baseline EDSS score and baseline Gd-enhancing T1 lesions (present, absent). The comparison of treatment groups will also be assessed using the log-rank test stratified by age at screening (>40, ≤40 years) and geographical region (US, non- US). Incomplete data will be imputed only for participants who complete the study, meet 3-month CDP criteria, and continue to meet criteria for EDSS disability progression through the final study assessment, but do not reach 6-month confirmation. For other participants without a confirmed 6-month CDP or with premature study discontinuation prior to 6-month confirmation after onset of an event, the participants will be censored at the date of last EDSS

#### Table 2 - Summary of primary estimand for main endpoints

#### 2 **ANALYSIS POPULATIONS**

The following populations for analyses are defined:

Population	Description
Enrolled	All participants who signed the ICF.
Randomly Assigned to Study Intervention/Randomized	All participants with a treatment kit number allocated and recorded in the IRT database, regardless of whether the treatment kit was used or not. Participants treated without being randomized will not be considered randomized and will not be included in any efficacy population.
ITT	The primary efficacy population will be the ITT population, defined as all randomly assigned participants. All efficacy analyses will be conducted according to the treatment group allocated by the randomization schedule, irrespective of the treatment received
Safety	All participants randomly assigned and exposed to study intervention, regardless of the amount of exposure, analyzed according to the treatment actually received.
	Randomized participants for whom it is unclear whether they took the study medication will be included in the safety population as randomized.
	The pharmacodynamic (PD) analyses will be performed on the safety population.
Pharmacokinetics	All participants in the safety population with at least one non- missing PK sample after first dose of the study intervention. Participants will be analyzed according to the treatment actually received.

#### Table 3 - Populations for analyses

ICF: informed consent form; ITT: intent to treat; PK: pharmacokinetic(s); IRT: interactive response technology

Participants exposed to study intervention before or without being randomized will not be considered randomized and will not be included in any analysis population. The safety experience of these participants will be reported separately.

For any participant randomized more than once, only the data associated with the first randomization will be used in any analysis population. The safety experience associated with any later randomization will be reported separately.

For participants receiving more than one study intervention during the study, the treatment group for as-treated analyses will be tolebrutinib 60 mg.

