6.2 STUDY INTERVENTION(S) ADMINISTERED

ARM name	SAR442168	Placebo	
Intervention name	SAR442168	Placebo	
Туре	Drug	Drug	
Dose formulation	Film coated tablet	Film coated tablet	
Unit dose strength(s)	60 mg	0 mg	
Dosage level(s)	Once daily	Once daily	
Route of administration	Oral	Oral	
Use	Experimental	Placebo	
IMP and NIMP	IMP	IMP	
Packaging and labeling	Study intervention will be provided in wallet blister packaging. Each wallet blister packaging will be labeled as per country requirements.	Study intervention will be provided in wallet blister packaging. Each wallet blister packaging will be labeled as per country requirements.	
Current name	SAR442168	Not applicable	

Table 2 - Overview of study interventions administered

IMP: investigational medicinal product; NIMP: noninvestigational medicinal product.

Between the protocol-scheduled on-site visits, interim visits may be required for IMP dispensing. As an alternative to these visits or to replace on-site IMP dispensation, if needed, SAR442168 may be supplied from the site to the participant via a Sponsor-approved courier company (direct-to-patient [DTP]) where allowed by local regulations and approved by the Sponsor.

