7 DISCONTINUATION OF STUDY INTERVENTION AND PARTICIPANT DISCONTINUATION/WITHDRAWAL

7.1 DISCONTINUATION OF STUDY INTERVENTION

7.1.1 Definitive discontinuation

The study intervention should be continued whenever possible.

Permanent intervention discontinuation is any treatment discontinuation associated with the definitive decision by the Investigator or the participant not to re-expose the participant to the study intervention at any time.

In rare instances, it may be necessary for a participant to permanently discontinue the study intervention. If study intervention is permanently discontinued, the participant will be asked to remain in the study to be evaluated until the EOS visit. For this set of participants (participants who discontinued the IMP and/or switched to other DMTs), no PK or biomarker samples will be collected after the pEOT visit, and MRI assessments will be performed only annually using the next annual visit as the starting point.

This will be important to continue to evaluate for safety and efficacy. See the SoA (Section 1.3) for data to be collected at the time of discontinuation of the study intervention. In the case that the study intervention is permanently discontinued, the participant should be treated for MS according to local clinical practice and the best judgment of the Investigator.

The following may be justifiable reasons for the Investigator or Sponsor to discontinue a participant from treatment:

- Adverse events that endanger the safety of the participant, or if discontinuation of study intervention is desired or considered necessary by the Investigator and/or participant.
- If IMP discontinuation criteria are met as per the guidance for the follow up of laboratory abnormalities (Appendix 2 [Section 10.2]).
- The participant is no longer deriving a therapeutic/clinical benefit in the opinion of the Investigator.
- If a female participant becomes pregnant or wishes to become pregnant during the study.
- At participant's request, ie, withdrawal of the consent for treatment.
- Any serious opportunistic infections (eg, PML [see Appendix 6 {Section 10.6}], HIV)
- Continued need for/chronic use of prohibited a concomitant medication (see Appendix 9 [Section 10.9]).
- Use of open-label SAR442168 or non-study disease modifying therapy approved for NRSPMS in their respective countries (eg, after 6-month CDP).

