## 1 INTRODUCTION

#### 1.1 STUDY DESIGN

This is a Phase 3, randomized, double-blind (DB), 2-arm, placebo-controlled, parallel group, multicenter, event-driven (6-month confirmed disability progression [CDP]) trial with a variable treatment duration (minimum of approximately 18 to 24 months) in participants with nonrelapsing secondary progressive multiple sclerosis (NRSPMS).

Approximately 1700 participants will be screened to achieve up to 1290 participants randomly assigned to study intervention.

After a screening period of up to 28 days, participants will be randomly assigned at a 2:1 ratio to receive 60 mg oral tolebrutinib or matching placebo daily. Randomization will be stratified by age at screening (>40 versus  $\leq$ 40 years) and geographic region (US versus non-US).

A month is defined as a period of 28 days by convention. As such, 6 months is defined as 24 weeks, 24 months as 96 weeks, and 48 months as 192 weeks.

Participants who complete the study intervention period (DB or open-label [OL] tolebrutinib if meeting 6-month CDP) may be offered the option to participate in a long-term safety (LTS) study. For participants who complete the study intervention period (DB or OL, if meeting 6-month CDP) and do not enter the LTS study, a final follow-up visit to collect safety data is performed 4 weeks after the last dose of study intervention. A participant is considered to have completed the study if he/she has completed all periods of the study including the end-of-study (EOS) visit, whether remaining on study intervention or not.

Study primary analysis will be conducted after study completion, when approximately 288 events of 6-month CDP have been observed, and final database lock.

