#### **Observation** period

The observation periods for safety will be divided into 4 epochs:

- The screening (pre-treatment) period is defined as the period from the signed informed consent date up to first administration of the study intervention.
- The **treatment period** (ie, treatment-emergent (TE) period) is defined as the period from the first administration of study intervention to
  - The earlier of last administration of the study intervention + 10 days or first IMP in the LTS study for participants not receiving tolebrutinib OL treatment,
  - The first administration of tolebrutinib OL treatment for participants switching to OL therapy

- The **OL period** (ie, OL TE period), applicable only for participants switching to tolebrutinib OL treatment, is defined as the time from first administration of tolebrutinib OL treatment to the earlier of last administration of OL treatment + 10 days or first IMP in the LTS study
- The **post-treatment period**, if applicable, is defined as the period from the end of treatment period (or end of OL period, if applicable) to the participant's final post-treatment study contact date.

Summaries of OL period data will be presented by original randomized treatment group and overall.

The on-study period is defined as the time from randomization until the end of the study defined as the last scheduled visit for those who completed the study and the end-of-study date collected on electronic case report form (e-CRF) page "Completion of End of Study" for those who did not complete the study. If death is the end-of-study reason, date of death will be used.

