#### 5.2 APPENDIX 2 PARTICIPANT DISPOSITIONS

The number (%) of participants included in each of the analysis populations listed in Table 3 will be summarized.

Screened subjects are those with a signed informed consent. Screen failures are defined as participants who consent to participate in the study but are not subsequently randomized. The number of screened participants will be summarized along with the number (%) of screen failures overall and by reason(s).

The number (%) of participants in the following categories will be provided:

- Exposed but not randomized, if applicable
- Randomized and not exposed, if applicable
- Randomized and exposed
  - Completed the DB study intervention period
  - Did not complete the DB study intervention period including main reason for discontinuation and reason for withdrawal by subject
  - Switched to the OL tolebrutinib treatment
  - Completed the OL period
  - Did not complete the OL period including main reason for discontinuation and reason for withdrawal by subject
- Completed the study
- Did not complete the study including main reason for study discontinuation
- Status at last contact (alive, dead)
- Entered LTS study

Reasons for permanent study intervention and study discontinuation, "adverse event" and "other reasons" will be split as related versus not related to COVID-19, if applicable.

For all categories of participants (except for nonrandomized) percentages will be calculated using the number of randomized participants as the denominator.

In addition, the number (%) of participants screened, screened-failed, randomized, with permanent study intervention discontinuation (DB and OL) and with early study discontinuation will be provided by country and site. Listings of other reasons for treatment discontinuation, and participants who are exposed but not randomized will be provided.

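### The as-treated rule in SAP section 2 is not limited to the double-blind period and makes no exception for the planned open-label switch, so read literally it puts placebo switchers in the tolebrutinib column of the double-blind safety tables

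*SAP*

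**What the plan says.** Below Table 3, SAP section 2 gives the rule for participants with two treatments: "For participants receiving more than one study intervention during the study, the treatment group for as-treated analyses will be tolebrutinib 60 mg". It names no period and does not mention the open-label switch.

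The other passages that bear on it are:

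- **Safety population (SAP section 2, Table 3).** Participants are included "regardless of the amount of exposure, analyzed according to the treatment actually received".
- **Period definitions (SAP 3.1, Observation period).** For switchers the treatment-emergent period ends at "The first administration of tolebrutinib OL treatment for participants switching to OL therapy". On the open-label data the SAP says: "Summaries of OL period data will be presented by original randomized treatment group and overall".
- **Passages that count open-label as study intervention.** SAP 1.1 refers to "Participants who complete the study intervention period (DB or open-label [OL] tolebrutinib if meeting 6-month CDP"), and the disposition appendix (SAP 5.2) tabulates participants "with permanent study intervention discontinuation (DB and OL) and with early study discontinuation will be provided by country and site". Protocol section 6 defines study intervention broadly enough to include placebo and any product given under the protocol. Protocol 6.2 lists placebo beside SAR442168 in "Table 2 - Overview of study interventions administered".
- **Passages that treat the switch as leaving study intervention.** Protocol 7.1.1 lists among the reasons for stopping treatment "Use of open-label SAR442168 or non-study disease modifying therapy approved for NRSPMS in their respective countries". SAP 5.5 handles the switch as an exception within time to discontinuation of study intervention.

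Protocol 6.6.1 offers the switch to any participant who reaches 6-month CDP, so placebo participants are included.

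**The concern.** A placebo participant who moves to open-label tolebrutinib has, on the broad usage, received two study interventions during the study. The sentence then labels that person tolebrutinib 60 mg in every as-treated analysis, including the double-blind safety tables, although everything in their double-blind period happened on placebo. In the open-label tables the same person appears under placebo, the randomized group.

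The period rules do not cure this. They decide which events are counted, but they do not set the column or the denominator.

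The double-blind treatment-emergent events are the main focus of adverse event reporting (SAP 3.6.2). Moving placebo participants into the drug column pulls the two columns together, and the people moved are selected by a post-randomization event.

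The effect is stronger for adverse events leading to permanent discontinuation. Protocol 7.1.1 bars from open-label treatment anyone who ended treatment for a reason other than 6-month CDP. Switchers therefore add to the tolebrutinib denominator but bring essentially no such events, while placebo keeps its events in a smaller group.

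**Working it through.** **Step 1. Does the sentence reach switchers?** Placebo is a study intervention (Protocol 6 and 6.2). Open-label tolebrutinib falls within study intervention in SAP 1.1 and 5.2. The sentence has no period limit. Read literally, it does. It then disagrees with SAP 3.1, under which the double-blind period of a placebo switcher is placebo only.

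**Step 2. Design inputs (SAP 4, Protocol 9.2).** Up to 1290 randomized 2:1, so 860 tolebrutinib and 430 placebo; 2-year placebo event rate 23.6%; 10% annual discontinuation; 24 months' accrual plus 24 months' follow-up; hazard ratio 0.70; 288 events for 80% power.

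Reproducing the plan's figure: with 288 events, 2:1 allocation and two-sided alpha 0.05, Schoenfeld's formula gives power Φ(√(288 × 2/9) × |ln 0.70| − 1.96) = 81.4%, in line with the stated 80%. The design figures are not in dispute; they serve only to size the group affected.

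**Step 3. How many placebo participants could switch?**

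- Event hazard λ = −ln(1 − 0.236)/2 = 0.1346 per year.
- Dropout hazard η = −ln(0.90) = 0.1054 per year.
- λ + η = 0.2400, and λ/(λ + η) = 0.561.
- Follow-up u is uniform on 2 to 4 years.

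To have time to switch, a participant needs an onset, 6 months to confirmation, and some time left. Requiring confirmation at least 3 months before study end means an onset at least 0.75 years before the end, with the participant still in the study over that time:

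P = 0.561 × [1 − mean of exp(−0.2400(u − 0.75))] × exp(−0.75 × 0.1054) = 0.561 × (1 − 0.588) × 0.924 = 0.213

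0.213 × 430 = 91.7, about 92 (21%).

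Counting everyone confirmed by the last study day gives 102 after dropout during confirmation, or 108 without it. People confirmed that late could hardly start open-label treatment, so 92 is the better ceiling. At the reduced size of about 1100 (last participant followed 30 months) the same calculation gives 91 of 367 (25%).

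Uptake is not stated, so the number relabelled, n, runs from near 0 to 92.

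**Step 4. Effect on a risk difference.** If switchers carry the average placebo risk, the placebo risk is unchanged and the difference is multiplied by 860/(860 + n).

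- n = 92: 860/952 = 0.903, so it shrinks by 9.7%.
- Illustration with assumed risks of 10% and 6%: the tolebrutinib column reads (0.10 × 860 + 0.06 × 92)/952 = 9.6%, and 4.0 points becomes 3.6.

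**Step 5. Effect on adverse events leading to discontinuation.** With no such events among switchers, the relative risk is multiplied by [860/(860 + n)] / [430/(430 − n)].

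- n = 92: (860/952)/(430/338) = 0.903/1.272 = 0.71, so it is 29% lower.
- n = 46 (half of the ceiling): (860/906)/(430/384) = 0.85, so it is 15% lower.

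At the reduced size, with n = 91, the two ceilings become 11% and 33%.

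**The case against.** The best reply is that the sentence was never meant for the planned switch. Its neighbours in SAP section 2 deal with irregular cases: exposure without randomization, and randomization more than once. Protocol 7.1.1 and SAP 5.5 treat the switch as leaving study intervention. SAP 3.1 gives open-label treatment its own period, and the safety sections summarize the two periods separately. This stands as evidence of intent. It does not settle the wording, because the documents use the term both ways and this is the only explicit rule for people with two treatments.

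A second reply is that the sentence does not contradict the treatment-received rule in Table 3 but serves as its tie-break for someone who received two treatments. That is fair. The real inconsistency is with the period rules in SAP 3.1.

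Third, the size is easy to overstate. Participants may stay on double-blind treatment or choose another therapy, must first clear liver and alcohol criteria (Protocol 6.6.1), and cannot switch if they had already ended treatment for another reason (Protocol 7.1.1). The plan's assumptions also yield about 304 events at 1290 participants, so a stop near 288 would come a little earlier. All of this makes 92 an upper bound. Average placebo risk among switchers is also unverified, since they are a selected group whose double-blind time ends early.

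A reader might also infer that pharmacodynamic (PD) data taken after the switch need separate handling. The documents do not support that here. Protocol 8.6 stops several samples once IMP is discontinued, so how many post-switch samples exist is unclear. Contamination after the switch is in any case a different question from the group label.

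**Conclusion.** The point holds as a wording defect: a stated rule which, followed literally, gives a wrong column label for placebo switchers in the double-blind safety tables.

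A reader might infer that those tables will in fact be produced that way. The documents do not show this, and the surrounding text points to a narrower intent. What they lack is a sentence that says so.

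At the full planned size, 0 to about 92 of 430 placebo participants (up to 21%) could be relabelled. Double-blind risk differences would shrink by 0 to about 10%, and the relative risk of adverse events leading to discontinuation would fall by up to about 29%. These figures rest on the plan's constant hazards, a cut-off of 3 months before study end, average placebo risk among switchers for the risk difference, and no discontinuation events among switchers for the relative risk.

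Efficacy is unaffected because it follows the randomized arm (ITT). Open-label tables are unaffected, and no safety testing is planned. It is still worth fixing before unblinded tables are run, because choosing between two readings afterwards would be open to challenge.

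**What to change.** Replace the sentence in SAP section 2 with wording to this effect:

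> Participants who take both tolebrutinib and placebo within the double-blind treatment period (for example through a dispensing error) are assigned to tolebrutinib 60 mg in as-treated analyses. The planned switch to open-label tolebrutinib after 6-month CDP leaves the treatment group unchanged for double-blind summaries and for the actual treatment group used in the PD summaries (section 3.7.2).

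The cost is two sentences in the SAP and one derivation rule in the programming. No new data are needed and no clinical rule changes.
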